3.1.3 Safety Endpoints

All AEs and serious AEs (SAEs) will be collected from beginning of surgery (defined as entry into OR) to POD-30.

1. Comparison of the incidence of serious treatment-emergent adverse events (TEAEs), individually and as composite where appropriate (e.g., TEEs, major adverse cardiac events), between the *Octaplex* and FP groups.
2. Comparison of the duration of mechanical ventilation (measured as duration of ventilation and ventilator-free days) up to POD-30 between the *Octaplex* and FP groups.
3. Comparison of the duration of ICU stay up to POD-30 between the *Octaplex* and FP groups.
4. Comparison of the duration of hospitalisation up to POD-30 between the *Octaplex* and FP groups.
5. Comparison of the incidence of death up to POD-30 between the *Octaplex* and FP groups.
6. Comparison of the number of days alive and out of hospital at POD-30 between the *Octaplex* and FP groups.

3.2 Overall Study Design and Plan

This is a multicentre, randomised, active-control, prospective, Phase 3 study in adult cardiac surgery patients. Approximately 500 patients will be randomised at approximately 12 hospitals (10 in Canada and two in the United States), and the study will require

approximately two years to complete. The study is planned to start in quarter 4, 2022 and to be completed in quarter 4, 2024.

The study will include adult (≥ 18 years old) patients who undergo cardiac surgery on CPB and require coagulation factor replacement due to bleeding post-CPB and after adequate reversal of heparin with protamine (as assessed by the surgical staff based on clinical and laboratory criteria) during surgery, and who have a known (e.g., as indicated by INR) or suspected coagulation factor deficiency. Patients will be randomised to receive either 4-factor PCC (*Octaplex*) or FP when the blood bank/pharmacy receives the first order for coagulation factor replacement and determines patient eligibility with the study team based on the study inclusion and exclusion criteria.

Following confirmation of eligibility, the technologist will randomise the patient to PCC or FP according to the randomisation and dosing schedule and prepare and release the IMP in a tamper sealed container. Operating room personnel will remain blinded until the decision to administer the IMP is made.

[figure not shown]
IMP can be administered if bleeding is severe enough to necessitate IMP (meaning at least a grade 2 level [moderate] bleeding according to the validated Bleeding Severity Scale [78]), heparin is adequately reversed (confirmed by the return of post-protamine activated clotting time [ACT] to within 10% of pre-pump ACT) and INR is ≥ 1.5 . IMP can also be administered if bleeding is severe enough to require urgent therapy, in which case treatment can be initiated irrespective of the INR value. Once the decision is made to administer the IMP, the administering clinician will break the seal on the container, carry out routine safety checks and initiate IMP administration according to the weight-based dosing recommendations.

The recommended initial dose for *Octaplex* will be 1500 IU for patients weighing ≤ 60 kg and 2000 IU for patients weighing >60 kg. The recommended initial dose for FP will be 3 U for patients weighing ≤ 60 kg and 4 U for patients weighing >60 kg.

A second dose of IMP can be administered if the patient continues to have at least moderate bleeding and suspected coagulation deficiency (e.g., INR ≥ 1.5) after completion of the first dose. If an order for a second dose of coagulation factors is received within 24 hours after IMP initiation (either from the operating room or in the ICU after surgery), the blood bank/pharmacy technologist will release the IMP as determined by the randomisation schedule up to the maximum allowable dose (*Octaplex* 3000 IU if ≤ 60 kg or 4000 IU if >60 kg; FP 6 U if ≤ 60 kg or 8 U if >60 kg) (a tamper-sealed container will not be used for these orders as clinicians will by now be unblinded).

If further doses of coagulation factors are required after the second dose of IMP, all patients will receive non-IMP FP. That is, for subsequent orders once the maximum dose of IMP has been administered (i.e., 2 doses), or after the 24-hour treatment period has elapsed, the technologist will release FP for both groups (in 1–4 U increments as per the ordering physician); these additional FP units will not be counted as part of the IMP (**Figure 1**).

Transfusion of non-IMP blood components and all haemostatic agents will be according to a standardised transfusion management algorithm (**Figure 2**). Measurements of INR and haemoglobin will be performed at preestablished time points, if not available already. No other aspects of routine clinical care will be modified.

Figure 1: Study Flow¹ FP in 1U increments as per the ordering physician

PCC, prothrombin complex concentrate; FP, frozen plasma; BW, body weight; IU, international units;

3.3 Discussion of Study Design and Choice of Control Group

3.3.1 Study Design

3.3.1.1 Criteria for Administration of IMP

The decision to administer the IMP will be based on objective clinical and laboratory criteria (**Section 6**). Incorporating these criteria in the study will standardise administration of IMP such that it is administered when clinically indicated.

3.3.1.2 Transfusion Protocol Standardisation

All participating hospitals will be required to follow an established transfusion management protocol for administration of non-IMP blood components and all haemostatic agents. Recognising that the intervention will occur during a very dynamic period (i.e., bleeding during surgery); however, the study employs a pragmatic design that will allow clinicians

to use best judgment within the context of the transfusion protocol. This will allow the surgical team flexibility while maintaining clinical practice standardisation that conforms to best clinical practices. This is important since other multicentre studies that have included a very strict design so far have failed when studied in later phase trials because of the inability of the sites to accurately follow the specified design, which itself has been criticised for not being consistent with usual clinical practice.

3.3.1.3 External Validity

This Phase 3 study will be performed in multiple hospitals with different characteristics. Moreover, patients will be randomised after the clinical team orders coagulation factor replacement and the only change to routine practice is dictating the choice of coagulation factor replacement amongst the two therapies that are currently available and used interchangeably. For these reasons, external validity should not be an issue.

3.3.1.4 Randomisation and Baseline Differences

Given the size of the study and random patient assignment stratified by centre, study groups should be reasonably balanced with respect to important clinical variables. The random allocation schedule will be prepared by a biostatistician not involved in the conduct of the trial, and neither the individual randomising nor any of the health care providers will know which treatment will be assigned to the patient when coagulation factor replacement is ordered.

3.3.1.5 Recruitment and Informed Consent

This is a pragmatic trial that compares two coagulation factor replacement therapies that are currently routinely used for the study indication in multiple regions globally and in various settings. It is not expected that participating in the trial will pose any risks to patients.

All patients ≥ 18 years old undergoing cardiac surgery with CPB at the study centres will be offered the chance to participate in the study prior to their surgery. Voluntarily given, written, informed consent will be obtained from the patient before the study procedures start. Once consent has been obtained and the patient enrolled into the study, eligibility according to inclusion criteria 1 and 4 (i.e., patients ≥ 18 years old, undergoing any index cardiac surgery employing CPB, who have provided informed consent) and the exclusion criteria will be confirmed. If screening is performed before the day of surgery, exclusion criterion 3 (i.e., severe right heart failure [clinical diagnosis \pm echocardiography]) will be rechecked on the day of surgery².

Only patients who require coagulation factor replacement therapy during surgery will be randomised, receive study drug, and undergo the proceeding visits and assessments. When the first order for PCC or FP is received by the blood bank/pharmacy while the patient is in the operating room, the blood bank/pharmacy technologist will confirm patient eligibility with the clinical team. Following confirmation of eligibility, the technologist will randomise the patient to PCC or FP according to the randomisation and dosing schedule.

²In Canada, informed consent will be obtained after randomisation, in accordance with Article 3.7A of the 2018 Tri-Council Policy Statement on the Ethical Conduct for Research Involving Humans.

Randomisation (1:1) will continue until at least 410 evaluable patients are obtained (205 patients per group).

3.3.1.6 *Blinding*

Given that the products have quite different physical properties, it is not possible to blind treating clinicians to group assignment. To minimise bias, treating clinicians will be blinded to group assignment until immediately prior to IMP infusion. The blood bank/pharmacy technologist will randomise the patient to PCC or FP, according to the randomisation schedule, and prepare and release the product in a tamper sealed container (with weight device in PCC boxes to ensure adequate concealment). The operating room personnel will be blinded to group allocation until the tamper lock seal is broken in the operating room immediately prior to infusion. For subsequent orders, a tamper-sealed container will not be necessary, and the blood bank/pharmacy technologist will release IMP as determined by the randomisation schedule, as per usual practice. The type of IMP administered will be recorded in manner that will not unblind the outcome assessor. Patients will also be unaware of treatment allocation. These same processes were successful in the pilot study noted above.

3.3.1.7 *Drop-outs and Crossovers*

Drop-outs: Based on the results of the FARES pilot study, it is anticipated that approximately 20% of randomised patients will not receive the IMP due to cessation of bleeding or identification of other causes of bleeding by the time the IMP is received in the operating room. (Significant dropouts are not anticipated for any other reasons, including not having undergone an index cardiac procedure.) Since clinicians will be blinded to group assignment until the decision is made to administer the IMP, and the decision to administer the IMP will be based on objective criteria, exclusion of these randomised but untreated patients from the primary analysis set will not bias the results. Study sample size has been calculated to compensate for dropouts. To ensure between-group comparability in baseline characteristics and outcomes, data will be collected for these patients for 30 days after surgery.

Product switching: Other than the coagulation factor replacement order being cancelled, all patients will be treated according to the randomisation schedule up to the maximum allowable dose during the treatment period (24 hours after IMP initiation). Thereafter, all patients will receive non-IMP FP when coagulation factor replacement is required. To ensure minimal product switching, instructions will be entered into the blood bank/pharmacy information system to dictate the randomisation product for the 24 hours after IMP initiation and will flag the laboratory technologists if attempts are made to override the instruction. In the FARES pilot trial, all treated patients received the appropriate IMP; thus, product switching is not anticipated to be a significant problem.

3.3.1.8 *Independent Data and Safety Monitoring Committee (IDSMC)*

An IDSMC will review accumulating safety, endpoint and other study data (recruitment, retention and compliance, data quality and timeliness, risk versus benefit).

The function of the IDSMC will be to protect and serve the recruited patients particularly pertaining to patient safety as well as to assist and advise the Sponsor on medical questions and issues of study conduct and continuation. The IDSMC will be independent of the investigating team and the Sponsor in operating and formulating recommendations.

The responsibilities of the IDSMC are listed in **Section 8.6**. The full role of the IDSMC will be detailed in the IDSMC Charter.

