9.1 Determination of Sample Size

The analysis of the primary efficacy endpoint will involve comparison of haemostatic treatment response to IMP, defined as 'effective' if no additional haemostatic intervention, such as administration of any systemic haemostatic agents (including platelets, cryoprecipitate, fibrinogen concentrate, activated recombinant factor VII, other coagulation factor products or a second dose of IMP) or any haemostatic interventions (including surgical re-opening for bleeding) is required from 60 minutes to 24 hours after initiation of the first dose of IMP.

Patients categorised as having an 'ineffective' haemostatic treatment response to IMP, due to requiring administration of any haemostatic intervention, including a second dose of IMP, in the time window from 60 minutes to 24 hours after initiation of the first IMP dose, will be considered as treatment failures.

Of the more than 100 patients studied in the FARES pilot study, approximately 75% of patients in the PCC group and 65% in the FP group demonstrated haemostatic treatment response from 60 minutes to 24 hours after initiation of the first IMP dose [58]. Using a more conservative estimate of 70% versus 65%, it is estimated that 410 patients will be required to demonstrate non-inferiority with a one-sided α of 0.025, power of $\geq 90\%$ and non-inferiority margin of 0.10 when using a Farrington-Manning score test.

It is anticipated that up to 20% of randomised patients may not meet administration criteria (based on objective Bleeding Severity Scale and INR) due to cessation of haemorrhage between randomisation and delivery of IMP to the operating room and therefore will not receive the therapy.

An administrative unblinded interim analysis will be carried out after 200 evaluable patients have been randomised and treated and will be used to re-estimate the sample size or stop for futility (non-binding) (**Section 9.4**). Patient recruitment will continue during the conduct of the interim analysis. The sample size in the second stage is limited to 210–800 evaluable patients. Accounting for drop-outs as described above, the total sample size will range between 513–1250 if the study is not stopped for futility at the interim (see table below).

	Stage 1	Stage 2 – Minimum	Stage 2 – Maximum	Total - Maximum
Evaluable patients	200	210	800	1000
Sample size including 20% dropouts	250	263	1000	1250

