9.2.1 Populations for Analysis

The full analysis set (FAS) will consist of all consented and randomised patients who receive any amount of the intervention, which will serve as the primary analysis set. A supporting efficacy analysis will be performed for the per-protocol set (PPS), which will exclude all patients with major deviations (e.g., patients who receive an IMP different to the IMP assigned by randomisation; patients who receive <50% of the planned dose; and patients who significantly violate inclusion/exclusion criteria). Randomised but untreated patients will not be included in the efficacy or safety analyses, but will be followed for 30 days to determine between-group comparability in baseline characteristics and outcomes.

A final decision about the classification of protocol deviations and their consequences regarding assignment of patients to analysis populations will be made during the data review meeting prior to the final analyses. All protocol deviations documented during the conduct of the study or identified at the data review process prior to database lock will be reviewed and classified as minor or major and with respect to their significance for the

planned analyses. This classification of protocol deviations is the joint responsibility of the clinical project manager, the study statistician, and Octapharma's responsible medical expert, and will be agreed and documented before the database is locked and the statistical analyses are performed.

The safety analysis population (SAF) will be identical to the FAS. In addition, to ensure that the safety reporting is complete, all haemostatic therapy and SAE data will be collected in cases where consent for remaining in the study cannot be obtained from Canadian sites due to logistical issues (e.g., patient died and a legally authorised representative could not be reached) and REB approval is obtained to collect the information. For Canadian patients who refuse consent, only treatment allocation data will be collected, and patients will not be included in any analyses.

The following subgroups will be analysed: sex (male/female); urgency (elective/non-elective surgery); and complexity (simple/complex surgery [procedures other than isolated ACB, single valve or repair of atrial septal defect]). Moreover, the impact of CPB duration on effectiveness will be evaluated by assessing treatment effect based on CPB duration increments.

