9.4 Interim Analysis

An administrative unblinded interim analysis will be carried out by an independent statistician when approximately 200 patients have been randomised and treated. Unblinded information will be communicated only to the IDSMC. Possible outcomes of this analysis and recommendations to the sponsor are:

- The study will be stopped for futility. The decision to stop for futility is non-binding.
- The sample size will be re-estimated by the independent statistician.

Patient recruitment will continue during the conduct of the interim analysis. The study cannot be stopped for efficacy at the interim analysis.

The sample size re-estimation will be based on the evaluation of the conditional power, calculated as described in section 7.3 of [94] making use of the observed response rates at the time of the interim analysis and inverse normal combination test statistic with equal weights given by

$$(\Phi^{-1}(1 - p_1) + \Phi^{-1}(1 - p_2))/\sqrt{2},$$

where p_1 and p_2 denote the p-values for testing the non-inferiority null hypothesis for the first and the second stage of the trial, respectively. The aspired conditional power used for the new intended sample size will be 90%.

A 20% drop-out rate will be added to the re-estimated sample size of evaluable patients to receive the number of patients to be enrolled in the second stage.

The minimum number of patients for the second stage is 210 evaluable subjects (even if the re-estimated sample size is below this number) or 263 including the possible dropouts (+20%). The sample size for the second stage cannot exceed 1250 patients (dropouts included). If the drop-out adjusted re-estimated sample size exceeds this threshold, the IDSMC may recommend to either stop the trial for futility or to enrol the maximum number of 1250 patients.

In addition, the IDSMC will review selected unblinded summary statistics every time 100 patients have completed the study (**Section 8.6**).

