#### 4.2. Sample Size

The analysis of the primary efficacy endpoint will involve comparison of haemostatic treatment response to IMP, defined as 'effective' if no additional haemostatic intervention, such as administration of any systemic haemostatic agents (including platelets, cryoprecipitate, fibrinogen concentrate, activated recombinant factor VII, other coagulation factor products or a second dose of IMP) or any haemostatic interventions (including surgical re-opening for bleeding) is required from 60 minutes to 24 hours after initiation of the first dose of IMP.

Patients categorised as having an 'ineffective' haemostatic treatment response to IMP, due to requiring administration of any haemostatic intervention in the time window from 60 minutes to 24 hours after initiation of the first IMP dose, will be considered as treatment failures.

Of the more than 100 patients studied in the FARES pilot study, approximately 75% of patients in the PCC group and 65% in the FP group demonstrated haemostatic treatment response from 60 minutes to 24 hours after initiation of the first IMP dose [13]. Using a more conservative estimate of 70% versus 65%, it is estimated that 410 patients will be required to demonstrate non-inferiority with a one-sided  $\alpha$  of 0.025, power of  $\geq 90\%$  and non-inferiority margin of 0.10 when using a Farrington-Manning score test.

It is anticipated that up to 20% of randomised patients may not meet administration criteria (based on objective Bleeding Severity Scale and INR) due to cessation of haemorrhage between randomisation and delivery of IMP to the operating room and therefore will not receive the therapy or will withdraw consent.

An administrative interim analysis will be carried out after approximately 50% of the target number of evaluable patients have been randomised and treated (100 patients enrolled in each group) and will be used to re-estimate the sample size or stop for futility (non-binding) (**Section**

**7.4).** The sample size in the second stage is limited to 210–800 evaluable patients. Accounting for dropouts as described above, the total sample size will range between 513–1250 if the study is not stopped for futility at the interim (see table below).

	Stage 1	Stage 2 – Minimum	Stage 2 – Maximum	Total - Maximum
Evaluable patients	200	210	800	1000
Sample size including 20% dropouts	250	263	1000	1250

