### **6.3. Full Analysis Set (FAS) Population**

The full analysis set (FAS) will be defined according to the intention-to-treat (ITT) principle and will consist of all randomised patients who provide consent and receive any amount of the intervention.

The FAS will serve as the primary analysis set. For patients who withdraw consent, data will be used up until the time consent is withdrawn.

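### Protocol and SAP assign different losses to the same 20% dropout allowance, and once re-estimation exceeds 210 nothing requires stage 2 to reach its evaluable target

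*Protocol*

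**What the plan says.** **The 20%.** Protocol 3.3.1.7, citing the pilot study, states that "it is anticipated that approximately 20% of randomised patients will not receive the IMP due to cessation of bleeding" or because another cause of bleeding is found. It adds: "Significant dropouts are not anticipated for any other reasons". Protocol 9.1 puts the share at up to 20% and names only untreated patients. SAP 4.2 repeats the 9.1 sentence but ends it with patients who "therefore will not receive the therapy or will withdraw consent". The rate does not change.

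**Who is evaluable.** Under SAP 6.3 the FAS "will consist of all randomised patients who provide consent and receive any amount of the intervention". Protocol 3.2 plans 10 hospitals in Canada and two in the United States. In Canada consent is obtained after randomisation. Protocol 9.2.1 states: "For Canadian patients who refuse consent, only treatment allocation data will be collected, and patients will not be included in any analyses". SAP 6.2 defines a separate population of treated Canadian patients whose consent could not be obtained.

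**How enrolment is set.** The synopsis runs stage 1 until 200 patients are evaluable. For stage 2, Protocol 9.4 adds 20% to the re-estimated evaluable number "to receive the number of patients to be enrolled in the second stage", and SAP 7.4 does the same. Protocol 3.3.1.5 and 4.1 continue the study to at least 410 evaluable patients. Protocol 6.2.2 counts the study complete at no fewer than 410 consented, randomised and treated patients.

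**The concern.** The SAP recognises a second kind of loss but leaves the rate as it was. If the protocol's figure for untreated patients is right, the 20% is used up before any treated patient is lost for lack of consent. The plan expects some such losses, since the SAP has a population for them.

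The re-estimation is meant to give 90% conditional power, calculated on evaluable patients. If enrolment stops at the inflated number and the true loss exceeds 20%, fewer evaluable patients reach the combination test than the calculation required. The type I error and the test itself are not affected. What is at stake is the power that the adaptive step is there to secure, and whether the stated randomised totals match the stated evaluable numbers.

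**Working it through.** **Inputs.** Response rates 70% v 65%, margin 0.10, "one-sided α of 0.025", power of at least 90% and stage 2 limits of 210-800 evaluable (Protocol 9.1). Conditional power target 90%, equal-weight inverse normal statistic (Protocol 9.4); critical value 1.96 (Protocol 9.2). Untreated share 20% (Protocol 3.3.1.7). *Assumption:* c is the share of treated patients who never enter the FAS because consent is refused or not obtained. The documents give no value, so 5%, 10% and 15% are shown.

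**1. The plan's own figures reproduce.** The Farrington-Manning formula gives 204.4, so 205 per arm and 410 in total, with power 90.1%. The equal-weight combination test with 200 + 210 gives 90.1% by formula and 90.2% by simulation (400,000 runs). Enrolment is N/(1 − 0.20): 200/0.80 = 250; 210/0.80 = 262.5, so 263; 800/0.80 = 1000. The totals are 250 + 263 = 513 and 250 + 1000 = 1250.

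**2. Reserve in the inflation.** With 20% untreated, 1000 enrolled gives 1000 × 0.80 = 800 treated, which is exactly the evaluable target. For both losses together to stay within 20%, the untreated share can be at most 1 − 0.80/(1 − c): 15.8%, 11.1% and 5.9% at c = 5%, 10% and 15%.

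**3. Yield in stage 2**, evaluable = enrolled × 0.80 × (1 − c):

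| Enrolled (target) | c = 5% | c = 10% | c = 15% |
|---|---|---|---|
| 500 (400, illustrative) | 380 | 360 | 340 |
| 1000 (800, maximum) | 760 | 720 | 680 |
| Enrolment needed for 800 | 1053 | 1112 | 1177 |

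**4. When re-estimation lies between 210 and 800.** Let z1 be the stage 1 statistic and b = 1.96 × √2 − z1 = 2.772 − z1. At the observed rates, 90% conditional power needs about n2 = 200 × ((b + 1.2816)/z1)².
- z1 = 1.35: 200 × (2.7035/1.35)² = 802.
- z1 = 2.0: 200 × (2.0535/2.0)² = 211.

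So the range 210-800 corresponds to z1 of about 1.35 to 2.0. Simulating stage 1 (400,000 runs, 100 per arm) and applying this formula puts the required number above 210 in about 40% of trials at 70% v 65%. In about 18% it is above 800, where the cap already prevents 90%. If both arms respond at 65%, it exceeds 210 in about 70%.

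**5. Conditional power after the shortfall** = Φ((b + 1.2816) × √(1 − c) − b):

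| z1 | c = 5% | c = 10% | c = 15% |
|---|---|---|---|
| 1.35 | 88.7% | 87.3% | 85.8% |
| 2.0 | 89.1% | 88.0% | 86.9% |

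The loss is about 1 to 4 percentage points.

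**6. The opposite direction.** If all losses total 15%, 1000 enrolled yields 1000 × 0.85 = 850 evaluable, 50 more than needed.

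**The case against.** **The minimum design is safe.** A reader might infer that 263 enrolled would leave stage 2 at 200, 189 or 179 evaluable instead of 210, with overall power below 90%. The documents do not support this. The rule to continue to at least 410 evaluable patients is a count that already requires consent, and 410 = 200 + 210. This part of the objection stands in full.

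**Withdrawal is not the loss that matters.** SAP 4.2 speaks of withdrawing consent, and a reader might infer that those patients leave the analysis. SAP 6.3 keeps their data up to withdrawal, and the estimand in SAP 10.1 scores discontinuation before 24 hours as non-response. The FAS loses only treated patients whose consent is refused or never obtained. This also stands.

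**Each document is coherent alone.** The protocol assumes 20% untreated and no other significant loss; the SAP assumes that both losses together reach at most 20%. A deficit appears only when the protocol's untreated share is combined with an additional consent loss. Protocol 9.1 and SAP 4.2 say up to 20%, which may leave slack. So it cannot be said that the inflation must under-deliver, only that it has no reserve if the estimate in Protocol 3.3.1.7 is correct.

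**There is oversight.** The data monitoring committee reviews recruitment and retention after every 100 completers and may recommend changes. That helps, but it does not replace a stated rule. The 410 floor also does not move when re-estimation raises the target.

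**Conclusion.** The concern holds in a limited form and is minor. The two documents define the same 20% differently, whatever the consent loss proves to be. The 200 + 210 minimum is protected. The gap concerns trials in which the re-estimated stage 2 number exceeds 210, about 40% of them at the planning rates. There the only stated link from the evaluable number to enrolment is the fixed 20%.

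The size rests on three assumptions: the untreated share is 20%, consent loss comes on top of it, and enrolment stops at the inflated number. With consent loss of 5%, 10% or 15% of treated patients, 90% conditional power becomes about 89%, 87-88% or 86-87%, and the maximum stage 2 yields 760, 720 or 680 instead of 800.

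**What to change.** 1. In Protocol 9.4 and SAP 7.4, choose one rule. Either stage 2 randomises until the re-estimated number of FAS patients is reached, within 210-800 evaluable; or planned stage 2 enrolment is that number divided by the stage 1 ratio of FAS to randomised patients, pooled over arms. For the ratio, count only patients whose consent status is resolved, because SAP 6 allows Canadian consent to be sought during follow-up.
2. Use one definition of dropout (untreated, consent refused, or consent not obtained) in Protocol 3.3.1.7, Protocol 9.1 and SAP 4.2. State that 513-1250 holds only if all losses total 20%.
3. Reconcile the stage 2 cap, which sets the available headroom. Protocol 9.1 and SAP 4.2 give 800 evaluable and 1000 enrolled, with 1250 as the overall total. Protocol 9.4 and SAP 7.4 allow 1250 enrolled in stage 2 alone, which is 1250 × 0.80 = 1000 evaluable.

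**Cost.** The change is one of wording, and the pooled ratio needs no unblinding. The downside is that the randomised total becomes a projection. Near the cap it could exceed 1250: at c = 10%, reaching 800 evaluable needs 1112 enrolled in stage 2, and 250 + 1112 = 1362 even with stage 1 held at 250. More treated patients would need ethics approval under Protocol 10.4. If an enrolment cap is kept, the plan should say that it takes precedence and that 90% conditional power may then not be reached.
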